13.2. Appendix 2 – Columbia – Suicide Severity Rating Scale

Confidential Page 83 of 105

Confidential Page 84 of 105

22 September 2022

Confidential Page 85 of 105

22 September 2022

13.3. Appendix 3 – Clinical Global Impression – Severity (CGI-S)

Investigator Clinical Global Impression – Severity (to be completed at Visit 1)

Date completed (ad illin) //.	Date compl	eted (dd-mn	n-yr): /	1
--------------------------------	------------	-------------	----------	---

GLOBAL

Circle the number that best rates the subject's condition overall relative to your clinical experience with this patient population.

- 1 = normal, not at all ill
- 2 = borderline ill
- 3 = mildly ill
- 4 = moderately ill
- 5 = markedly ill
- 6 = severely ill
- 7 = among the most extremely ill

BEHAVIOR

Circle the number that best rates the subject's overall behavior relative to your clinical experience with this patient population.

- 1 = normal, not at all ill
- 2 = borderline ill
- 3 = mildly ill
- 4 = moderately ill
- 5 = markedly ill (
- 6 = severely ill
- 7 = among the most extremely ill

COGNITION

Jersely ill

Jersely ill

Generately ill

Gene

MOTOR ABILITIES

Circle the number that best rates the subject's overall motor ability relative to your clinical experience with this patient population.

- 1 = normal, not at all ill
- 2 = borderline ill
- 3 = mildly ill
- 4 = moderately ill
- 5 = markedly ill
- 6 = severely ill
- 7 = among the most extremely ill

Confidential Page 86 of 105

22 September 2022

Parent/Caregiver Clinical Global Impression – Severity (to be completed at Visit 1 via interview of the parent/caregiver)

22 12			7.2	
Date comp	hatai	(dd-mm-vr):	/ /	
Date Cullic	neteu	luu-iiiii-vii.	, ,	

GLOBAL

Circle the number that the parent/caregiver states best rates their impression of the subject's condition overall relative to their expectations for age and development.

- 1 = normal, not at all ill
- 2 = borderline ill
- 3 = mildly ill
- 4 = moderately ill
- 5 = markedly ill
- 6 = severely ill
- 7 = among the most extremely ill

COGNITION

...oderately ill
o = markedly ill
6 = severely ill
7 = among the most extremely ill
7 Circle the number that the parent/caregiver

BEHAVIOR

Circle the number that the parent/caregive states best rates their impression of the subject's overall behavior relative to their expectations for age and development.

- 1 = normal, not at all ill
- 2 = borderline ill
- 3 = mildly ill
- 4 = moderately il
- 5 = markedly ill
- 6 = severely if
- 7 = among the most extremely ill

MOTOR ABILITIES

Circle the number that the parent/caregiver states best rates their impression of the subject's overall motor ability relative to their expectations for age and development.

- 1 = normal, not at all ill
- 2 = borderline ill
- 3 = mildly ill
- 4 = moderately ill
- 5 = markedly ill
- 6 = severely ill
- 7 = among the most extremely ill

Confidential Page 87 of 105

22 September 2022

13.4. Appendix 4 – Clinical Global Impression – Improvement (CGI-I)

Investigator Clinical Global Impression - Improvement

Date com	pleted	(dd-mm-yr):	1 1
Dute com	JI CLOU	MM IIIIII YI /.	

GLOBAL

Circle the number that best rates how subject's overall condition has improved or worsened relative to the rating provided at Visit 1.

- 1 = very much improved
- 2 = much improved
- 3 = minimally improved
- 4 = no change
- 5 = minimally worse
- 6 = much worse
- 7 = very much worse

me number that best rates how the subject's **overall cognition** has improved or worsened relative to the rating provided at Visit 1.

1 = very much improved
2 = much improved
3 = minimally improved
1 = no change
= minimally rise document cathor and any extensive this document cathor and any extensive the cathor and extensive t

BEHAVIOR

Circle the number that best rates how the subject's overall behavior has improved or worsened relative to the rating provided at Visit 1.

- 1 = very much improved
- 2 = much improved
- 3 = minimally improved
- 4 = no change
- 5 = minimally worse
- 6 = much worse
- 7 = very much worse

MOTOR ABILITIES

Circle the number that best rates how the subject's overall motor ability has improved or worsened relative to the rating provided at Visit 1.

- 1 = very much improved
- 2 = much improved
- 3 = minimally improved
- 4 = no change
- 5 = minimally worse
- 6 = much worse
- 7 = very much worse

Confidential Page 88 of 105

22 September 2022

Parent/Caregiver Clinical Global Impression – Improvement (to be completed via interview of the parent/caregiver)

Date comp	leted (dd-mm-vr): / /

GLOBAL

Circle the number that the parent/caregiver states best rates their impression of how the subject's overall condition has improved or worsened relative to the rating provided at Visit 1.

- 1 = very much improved
- 2 = much improved
- 3 = minimally improved
- 4 = no change
- 5 = minimally worse
- 6 = much worse
- 7 = very much worse

COGNITION

se control and any series document cannot be adonated any series of the series of the

BEHAVIOR

Circle the number that the parent/caregiver states best rates their impression of how the subject's overall behavior has improved or worsened relative to the rating provided at Visit 1.

- 1 = very much improved
- 2 = much improved
- 3 = minimally improved
- 4 = no change
- 5 = minimally worse
- 6 = much worse
- 7 = very much worse

MOTOR ABILITIES

Circle the number that the parent/caregiver states best rates their impression of how the subject's overall motor ability has improved or worsened relative to the rating provided at Visit 1.

- 1 = very much improved
- 2 = much improved
- 3 = minimally improved
- 4 = no change
- 5 = minimally worse
- 6 = much worse
- 7 = very much worse

Confidential Page 89 of 105

Appendix 5 – Maximum Allowable Blood Draw Volumes 13.5.

Maximum allowable blood draw volumes:

PATIENT'S	WEIGHT			
Ka	WEIGHT.	TOTAL VOLUME	MAXIMUM mL IN ONE BLOOD DRAW	MAXIMUM mL IN A 30-DAY PERIOD
1.9	lbs	mL	2.5% of total blood vol	5% of total blood vol
1	2.2	100	2.5	5
2	4.4	200	5	10
3	3.3	240	6	12
4	8.8	320	8	16)
5	11	400	10	20
6	13.2	480	12	24
7	15.4	560	14	28
8	17.6	640	16 2	32
9	19.8	720	18	36
10	22	800	20	40
11 thru 15	24 thru 33	880-1200	22-30	O 44-60
16 thru 20	35 thru 44	1280-1600	32-40	64-80
21 thru 25	46 thru 55	1680-2000	42-50	64-100
26 thru 30	57 thru 66	2080-2400	52-60	104-120
31 thru 35	68 thru 77	2480-2800	62-70	124-140
36 thru 40	79 thru 88	2880-3200	72-80	144-160
41 thru 45	90 thru 99	3280-3600	82-90	164-180
46 thru 50	101 thru 110	3680-4000	92-100	184-200
51 thru 55	112 thru 121	4080-4400	102-110	204-220
56 thru 60	123 thru 132	4480-4800	112-120	224-240
61 thru 65	134 thru 143	4880-5200	122-130	244-260
66 thru 70	145 thru 154	5280-5600	132-140	264-280
71 thru 75	156 thru 165 📿	5680-6000	142-150	284-300
76 thru 80	167 thru 176	6080-6400	152-160	304-360
81 thru 85	178 thru 187	6480-6800	162-170	324-340
86 thru 90	189 thru 198	6880-7200	172-180	344-360
91 thru 95	200 thru 209	7280-7600	182-190	364-380

Based on blood volume of:

1 to 2 kg 100 mL/kg (pre-term infant)

Confidential Page 90 of 105

22 September 2022

13.6. Appendix 6 - Study Conduct During COVID-19

pact been 1 be es In March 2020, the World Health Organization declared a global pandemic related to an illness caused by a novel coronavirus known as COVID-19. As a result, public health initiatives, such as laws, regulations and policies were enacted at country and institutional levels to protect the health of the general public. These initiatives and policies have affected the ability of study sites to conduct the trial per protocol and the ability of the sponsor and/or delegate to conduct trial oversight and monitoring visits.

In an effort to support the rights, safety and welfare of subjects and ensure as little impact on the integrity of the research as possible the following alternative processes have been implemented due to restrictions related to COVID-17. 1100g...
made to conduct study visits per protocol, any implementation of alternative processes

1. Allowance of Delays to In-person Study Visits

If sites are unable to conduct study visits, or subjects are unable to travel to the study site due to COVID-19 circumstances, an in-person visit may be delayed up to 6 weeks from the protocol-defined visit due date. Data will need to be entered per normal procedures in the EDC, with a description indicating COVID-19 as the cause for delay in response to queries. If a subject is unable to travel to the study site within this expanded 6-week window, a telephone or video telemedicine visit should be attempted, as described below. If a telephone or video telemedicine visit cannot be conducted in the 6-week window, the visit should be considered missed and the next scheduled visit conducted

2. Allowance of Remote Telemedicine/Telephone/Video Visits:

Visit 1 should be conducted in person. For Visits 2 through 6, remote visits via telephone or video are acceptable when subjects are unable to travel to the site for in-person visits due to COVID-19 circumstances. The following information should be collected and recorded in the source documentation and in the EDC where applicable. Log pages (e.g. AEs, concomitant medication changes) will be entered normally as they are not associated with specific visits; assessment forms located within a particular visit page will also be entered normally, however, a "telemedicine visit" button will be available for selection on the overall visit page to capture the basis for missing or alternatively collected (i.e. remote) data. Detailed instruction for EDC entry may be found in the CRF Completion Guidelines (CCGs).

- Date and time of the telephone/video visit
- Any changes in health status
- AEs/SAE assessment
- Concomitant medication query
- Seizure assessment (by Investigator) when possible
- Scales and Questionnaires, when applicable and if feasible
 - C-SSRS
 - CGI-I (Global and Symptomatic, by Investigator and Parent/Caregiver)

Confidential Page 91 of 105

22 September 2022

3. End-of-Study/Early Termination (EOS/ET) and Follow-up Visits:

Cardiac follow-up visits must be conducted in-person.

For the EOS/ET visit and Post-Dosing Follow-up visits (ie, 2 weeks after the last dose), every attempt should be made to conduct these visits in-person. For subjects tapering off study-drug that are unable to come to the study site, the EOS/ET and Post-Dosing Follow-up visits may be conducted via telephone or video. However, subjects should return to the study site in person, as soon as feasible to conduct any safety assessments that were unable to be evaluated remotely. If an in-person visit cannot be scheduled within 6 months of the EOS/ET and/or Post-Dosing Follow-up visit windows, these visits will be considered as missed.

The telephone or video visits will collect the following data, at minimum:

- Date and time of the telephone/video visit
- Any changes in health status
- AEs/SAE assessment
- Concomitant medication query
- Seizure assessment (by Investigator) when possible

EOS/ET for subjects transitioning to Commercial drug:

For the EOS/ET visit (Visit 7) and Post-Dosing Follow-up visit (Visit 8), every attempt should be made to conduct these visits in-person. For subjects tapering off study-drug that are unable to come to the study site, the EOS/ET and Post-Dosing Follow-up visits may be conducted via telephone or video. However, subjects should return to the study site in person, as soon as feasible to conduct any safety assessments that were unable to be evaluated remotely. Subjects who transition to commercially available drug must have had an ECHO within 3 to 6 months before the transition date. Subjects who transition to commercially available drug will have follow-up ECHOs within the required timeframe while on commercial drug.

4. Allowance of delays to ECHO, ECG, Chest X-Ray, EEG and clinical lab assessments when in-person study visits are missed or delayed

If it is not possible to obtain the assessments as described below, a documented risk/benefit discussion with the CRO medical monitor is required to determine a course of action, which may include approval to delay further for a pre-specified duration, subject withdrawal, or other actions. The risk/benefit analysis will take into account AEs, previous assessment findings, duration of delay, clinical improvement while on study drug (seizure and non-seizure outcomes), and region-specific risk of attending in-person visits to complete the assessments.

Doppler ECHO:

If subjects are unable to travel to the study site due to COVID-19 circumstances, ECHOs may be delayed up to an additional 3 months from the protocol-designated ECHO due date (for a total of 9 months from the time of the last ECHO) for subjects that exhibited the

Confidential Page 92 of 105

22 September 2022

following on their previous, most recent ECHO: absent aortic regurgitation, absent or trace mitral regurgitation, and PASP <30 mmHg.

All subjects with regurgitation \geq trace aortic regurgitation, \geq mild mitral regurgitation, or PASP ≥30 mmHg may have ECHO delayed from the protocol-designated ECHO due date by up to 6 weeks only.

ed althorization In those cases where an ECHO cannot be performed in the specified time period at the study-authorized facility by a certified sonographer, the Sponsor may approve administration of the ECHO at an alternative facility to minimize subject's need for travel. If the ECHO cannot be performed, a risk/benefit analysis must be conducted as described above.

If a delayed ECHO was conducted within 30 days of a scheduled Cardiac Follow-up Visit and there were no findings meeting Level 2 criteria (see Protocol Table8) the Cardiac Follow-up Visit may be skipped. If Level 2 or greater findings were observed, then the Cardiac Follow-up Visit should be re-scheduled from the date of the delayed ECHO

ECG, Chest X-ray and EEG:

If clinically indicated and where applicable, delays in these assessments may be implemented based on the investigators' clinical discretion, weighing the risk/benefit of the clinical necessity of the assessment versus the risk of an in-person visit. All decisions should be documented appropriately in the source documentation. If not conducted at the study site, ECG, chest X-ray and EEG can be performed at any qualified local facility with results to be sent to the Principal Investigator for safety overread and documentation.

If the ECG (or in the case of certain country-specific regulations: Chest X-ray or EEG) was conducted within 30 days of a scheduled Cardiac Follow-up Visit, these assessments do not need to be repeated at the Cardiac Follow-up Visit provided there were no significant findings that require additional follow-up.

Clinical Laboratory Assessments

Laboratory assessments may be delayed up to 6 weeks. If further delay is required, and they are clinically indicated by the investigator, laboratory assessments may be conducted at local laboratory facilities. Local lab results are to be sent to the Principal Investigator for safety overread.

If results from the most recent assessments are within normal range or documented as clinically insignificant, further delays to obtaining laboratory assessments may be implemented based on clinical judgmental.

5. Alternative Dispensation for Study Drug

Shipments of investigational product may be sent by courier from site pharmacy to the subject's home via Sponsor-approved processes if the subject cannot or will not attend the dispensation visit(s). This shipment of drug should be arranged for patients who are due in the clinic for a drug dispensation visit. Other alternative dispensation, such as curbside pickup, may be implemented provided they are approved by the Sponsor and appropriate safeguards are taken to ensure compliance with existing regulatory requirements for maintaining investigational product accountability. Detailed instructions for drug handling, storage, accountability, etc. are described in the Pharmacy Manual.

Confidential Page 93 of 105

22 September 2022

13.7. **Appendix 7- Summary of Protocol Amendment 4.0**

Changes were made to protocol Amendment 3.1 to include updating the version number and date to Protocol Amendment 4.0 22 September 2022, as well as study number, sponsor signatories and affiliation, reflective its acquisition by UCB Pharma Inc. Language was modified to clarify how the end of study participation will occur. These changes required edits to the Synopsis. Schedule of Assessments, Sections 1.6, 3.1, 3.3, 6.1.3 and 10.4.

Further changes were made to the Synopsis, sections 3.7.1 and 4.4, 8.9.1 and 10.6 to reflect the opportunity to transfer of safety oversight back to the sponsor at any time during the study conduct.

Further updates were made to Section 1 to be updated with the newest information version of the ZX008 Investigator Brochure 2022 v10.0. Clarification was made on the affiliation of the study medical monitors throughout the document as well as on the result disclosure on public registries (Sections 2.3 and 8.5.1). Further changes included updating Section 8.6 to reflect the contact details for SAE reporting,

List of Specific Changes

Additions are marked in blue and red underline and deletions are marked in blue and red strikethrough. Minor editorial and non-substantive changes, such as the correction of typing or formatting errors, updated use of abbreviations, updating headers and footers, tables of contents, list of abbreviations, signature pages, etc., are not listed. Note that the list of specific changes below is presented in the order in which they first appear in the protocol, but several items are grouped by rationale.

1. Updates were made to the Synopsis, Section 1.6, 3.1, 3.3, 6.1.3 and Section 10.4 concerning

Confidential Page 94 of 105

22 September 2022

STUDY SYNOPSIS

Study Title: An Open-Label Extension Trial to Assess the Long-Term Safety of ZX008 (Fenfluramine Hydrochloride) Oral Solution as an Adjunctive Therapy for Seizures in Patients with Rare Seizure Disorders Such as Epileptic Encephalopathies Including Dravet Syndrome and Lennox-Gastaut Syndrome

Study Number: ZX008-1900

Study Product: Fenfluramine Hydrochloride Oral Solution, ZX008

e alhoritation Indication(s) Studied: Type of Study: Long-term safety Rare Seizure Disorders Such as Epileptic Encephalopathies. including Dravet syndrome and Lennox-Gastaut syndrome

Phase of Development: Phase III Countries: North America, Europe, Australia, and Japan

Sponsor: Zogenix International Limited

Co-Coordinating Investigator:

Estimated Duration of Individual Subject Participation:

Participation for subjects will be voluntary until approval of ZX008 has been obtained from regulatory authorities for the subject's indication, until a managed access program is established as allowed per countryspecific requirements in addition to legal and regulatory guidelines in the subjects' country of residence, or until the investigational product development for the subject's indication is stopped by the Sponsor, whichever comes first up to 36 months or until ZX008 is approved in a subject's country patient's health plan formulary, whichever occurs first.

Objectives:

The primary objective of the study is:

To assess the long-term safety and tolerability of ZX008

The secondary objectives of the study are:

- . To assess the effect of ZX008 on the following effectiveness measures:
 - Investigator assessment of convulsive seizure response (<25%, ≥25%, ≥50%, ≥75%, or 100% [ie, seizure-free] improvement)
 - Clinical Global Impression Improvement (CGI-I) rating, global and symptomatic, as assessed by the investigator
 - CGI-I rating, global and symptomatic, as assessed by the parent/caregiver

Methodology: This is an international, multicenter, open-label, long-term safety study of ZX008 in patients with rare seizure disorders, epiteptic encephalopathy, including Dravet syndrome or Lennox-Gastaut syndrome. Subjects eligible for participation are those with Dravet syndrome who are currently enrolled in Study ZX008-1503, or those with LGS who have successfully completed Study ZX008-1601-Part 2, and are candidates for continued treatment with ZX008 for an extended period of time, or those with Dravet syndrome, Lennox-Gastaut syndrome, or another epileptic encephalopathy who have completed participation in a Zogenix-sponsored study and have been invited to participate in this study. Participation in this OLE study is entirely voluntary

Subject will be eligible to participate in this trial until approval of ZX008 has been obtained from regulatory authorities for the subject's indication, until a managed access program is established as allowed per countryspecific requirements in addition to legal and regulatory guidelines in the subjects country of residence, or until the investigational product development for the subject's indication is stopped by the Sponsor, whichever comes first Our up to 36 months, or until ZX008 is approved in a subject's country of residence and listed on a patient's health plan formulary. Thus, the maximum duration for participation is 36 months.

Confidential Page 95 of 105

22 September 2022

Duration of Treatment:

All subjects will receive ZX008 until approval of ZX008 has been obtained from regulatory authorities for the subject's indication, until a managed access program is established as allowed per country-specific

Section 1.6

Rationale for Current Study

As described above, Zogenix has conducted 2 positive double-blind, randomized, placebo-controlled studies in Dravet syndrome. Additionally, long-term safety and efficacy data for up to 3 years in some subjects has been collected. Based on the results from Study 1 and Study 1504 in Dravet syndrome, Zogenix has submitted a New Drug Application (NDA) to the United States Food and Drug Administration, and a Marketing Authorization Application (MAA) in Suropean Medicines Agency. Zogenix also has one double-blind placebongoing in Lennox-Gastaut syndrome (Study 1601; NCT number CT03355209). This is a 2-part study. Part 1 is a distribution of the controlled study to assess the efficacy and rappy for seizures in children.

Piepri Pi

Confidential Page 26 of 98

ZX008, Fenfluramine Hydrochloride ZX008-1900 EP0215 Clinical Study Protocol Amendment 4.03-1

assessed from Part 1 data. Part 2 is a 1-year open-label, flexible-dose extension for subjects completing Part 1 of the study.

Study 1503 is soon to be completed, and Study 1601 Part 2 provideds treatment for up to 1 year. The main purpose of this open-label study is to continue to provide treatment to patients with Dravet syndrome or Lennox-Gastaut syndrome who may still derive clinically meaningful benefit from ZX008 after completing Study 1503 or Study 1601 Part 2, until the product is approved and available via prescription, or a managed access program is established as allowed per country-specific requirements in addition to legal and regulatory guidelines in the subjects country of residence, or until the investigational product development for the subject's indication is stopped by the Sponsor, whichever comes first.

This study (1) additionally provides an opportunity to continue to evaluate the long-term safety of ZX008 in Dravet syndrome and Lennox-Gastaut syndrome until the product is approved and available via prescription; and, (2) may serve as an open-label extension study for patients with rare seizure disorders and epileptic encephalopathies who have participated in other Zogenixsponsored clinical trials of ZX008.

Confidential Page 96 of 105

22 September 2022

Section 3.1

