8.9.1. Follow-up of Echocardiogram Findings

All ECHOs will be evaluated by a central reader from ERT, Inc. (ERT), in consultation with the ICAB, if warranted. Findings related to pulmonary hypertension or valvulopathy on any of the 4 valves (aortic, mitral, pulmonary, tricuspid) will be reported to the investigator with grades of normal, trace, mild, moderate, or severe. If the ECHO result has progressed in severity since the last reading, then new oversight measures will be enacted as described below in Levels 1-3. Table 8 describes the severity of ECHO findings with the level of increasing oversight if the subject is to remain in the study.

Table 8.	Clinical Measures Enacte	ed Upon	Increasing	Severity	of ECI	HO Findings

	Valve				
Severity	Aortic	Mitral	Pulmonary	Tricuspid	
Trace	Level 1	Level 1	Level 1	Level 1	
Mild (≤18 years)	Level 2	Level 1	Level 1	Level 1	
Mild (>18 years)	Level 2	Level 1	Level 1	Level 1	
Moderate	Level 3	Level 2	Level 2	Level 2	
Severe	Level 3	Level 3	Level 3	Level 3	

Level 1: Continue per protocol

Level 2:

- 1. If there is a desire to continue study medication:
 - a. The investigator will evaluate the efficacy to date based on study diaries if available and consult with the parent/guardian, and determine whether study treatment was associated with significant, meaningful benefit in number, severity and/or duration of seizures and/or on the impact on daily functioning.
 - b. The investigator will consider whether the subject has had reasonable trials (dose and duration) of other available anticonvulsants (eg, VPA, CLB, or topiramate), alone or in combination, and not maintained the level of seizure control achieved with study medication.
- 2. If the investigator feels consideration of continued treatment is warranted considering benefit and potential risk, and the parent/guardian feels strongly that the subject be maintained on the study medication when understanding the risks, the parent/guardian

Confidential Page 63 of 105

22 September 2022

must sign a new consent which describes the additional risk and the subject should provide assent if appropriate.

- a. If both of these conditions are not met, the subject is discontinued from treatment.
- 3. The investigator prepares a case history and rationale for continuation to be submitted to the IDSMC or Sponsor safety representative/physician for review, including consideration of effects on seizures and comorbidities.

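### The COVID-19 ECHO delay rule in Appendix 6 leaves out the tricuspid and pulmonary valves, so an isolated Level 2 or 3 finding there can wait longer for its next ECHO than a Level 1 aortic or mitral finding (minor)

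*Protocol*

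**What the plan says.** ECHO is scheduled every 6 months (protocol Table 1, footnote d). For subjects who cannot travel because of COVID-19, Appendix 6 (Section 13.6), item 4 says that "ECHOs may be delayed up to an additional 3 months from the protocol-designated ECHO due date", which it sums up as "for a total of 9 months from the time of the last ECHO". The condition is that the subject showed the "following on their previous, most recent ECHO: absent aortic regurgitation, absent or trace mitral regurgitation, and PASP <30 mmHg". Subjects with trace or greater aortic regurgitation, mild or greater mitral regurgitation, or PASP of 30 mmHg or more "may have ECHO delayed from the protocol-designated ECHO due date by up to 6 weeks only".

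Elsewhere the protocol uses all four valves:

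- Section 8.9.1 states that "Findings related to pulmonary hypertension or valvulopathy on any of the 4 valves (aortic, mitral, pulmonary, tricuspid) will be reported to the investigator". Its Table 8 assigns each valve and grade to an oversight level. Moderate pulmonary or tricuspid findings are Level 2 and severe ones Level 3. Trace aortic and mild mitral findings are Level 1, which calls for no extra measures.
- Table 5, footnote a (Section 6.3) counts regurgitation of moderate or higher grade on the pulmonary or tricuspid valve as a cardiac sign that needs extended follow-up.
- Appendix 6, item 4 itself uses Table 8 a little further on. If a delayed ECHO falls within 30 days of a scheduled cardiac follow-up and "there were no findings meeting Level 2 criteria (see Protocol Table8) the Cardiac Follow-up Visit may be skipped".

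**The concern.** The delay rule sorts subjects by risk, but it looks at two valves and a pressure, while the protocol's ranking looks at four valves. Followed exactly, it can give the longer wait to a subject whom Table 8 places under closer oversight, and the shorter one to a subject for whom Table 8 asks nothing further.

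This matters because long-term safety is the primary objective, fenfluramine was withdrawn in the late 1990s over cardiac valve abnormalities (Section 1.2), and the 6-monthly ECHO is the scheduled check on the valves. At stake is the timing of a safety examination for individual subjects. No estimate or test depends on it.

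**Working it through.** **Inputs.** Routine interval of 6 months (Table 1, footnote d); delays of 3 months and 6 weeks (Appendix 6, item 4); levels by valve and grade (Table 8). One month is taken as 30 days.

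**The plan's own figure.** 6 + 3 = 9 months, as Appendix 6 states.

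**Is there a third category?** The 3-month condition is: aortic absent, and mitral absent or trace, and PASP below 30 mmHg. Its negation is: aortic trace or more, or mitral mild or more, or PASP of 30 mmHg or more. That is exactly the 6-week condition. The two sets are complements, so nothing else in the rule catches tricuspid or pulmonary regurgitation.

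**Isolated findings with PASP below 30 mmHg:**

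| Finding on the last ECHO | Table 8 level | Permitted delay |
|---|---|---|
| Aortic, trace | 1 | 6 weeks |
| Mitral, trace | 1 | 3 months |
| Mitral, mild | 1 | 6 weeks |
| Aortic, mild | 2 | 6 weeks |
| Mitral, moderate | 2 | 6 weeks |
| Tricuspid or pulmonary, trace or mild | 1 | 3 months |
| Tricuspid or pulmonary, moderate | 2 | 3 months |
| Tricuspid or pulmonary, severe | 3 | 3 months |

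The last two rows are out of order. With PASP of 30 mmHg or more, every finding is held to 6 weeks and the problem does not arise.

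**Size on the 6-monthly schedule:**

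- 3-month delay: 180 + 90 = 270 days, or 9.0 months.
- 6-week delay: 180 + 42 = 222 days, or 222/30 = 7.4 months.
- Difference: 270 − 222 = 48 days. Ratio: 270/222 = 1.22.

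SAP Table 3 gives France an ECHO every 3 months, so these totals do not apply there.

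**Effect of the fix on grade patterns.** Use five grades per valve (absent to severe) and PASP below 30 mmHg. The patterns that qualify for 3 months number 1 (aortic) × 2 (mitral) × 5 × 5 = 50. Those with both right-sided valves at mild or less number 2 × 3 × 3 = 18, all at Level 1 or with no finding. The other 50 − 18 = 32 contain a Level 2 or 3 finding. Of these, 2 × (25 − 16) = 18 are Level 3 and 2 × (16 − 9) = 14 are Level 2. Excluding Level 2 or greater on any valve takes the 32 to 0 and leaves the 18 unchanged. These are counts of possible patterns, not of subjects.

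**The case against.** The strongest reply is that such a subject would hardly ever be on drug with an unchanged 6-monthly schedule. Exclusion criterion 2 can bar current valvulopathy at entry. Section 4.4 requires discontinuation when regurgitation on any of the four valves is judged to outweigh the benefit. Under Section 8.9.1, continuing at Level 2 or 3 needs the investigator's justification, a new consent, an evaluation by the cardiology board and a determination by the IDSMC or Sponsor. Level 3 also needs a consistent seizure improvement of more than 75%. The outcomes listed for that review are stopping the drug, more frequent ECHO and ECG, added measures, or a lower dose. The delay is itself only permitted, not prescribed.

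Most of this stands, and it is why the point is minor. It does not close the gap:

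- More frequent ECHO is one possible outcome of the review, not an automatic one.
- The review is prompted by progression since the last reading, so a stable moderate finding need not lead to a new one before a delay.
- The added safeguard in Appendix 6 does not reach this case: "If it is not possible to obtain the assessments as described below, a documented risk/benefit discussion with the CRO medical monitor is required". A delay inside the 3 months is within what is described.
- PASP is a pressure. It does not grade tricuspid or pulmonary regurgitation.

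The focus on the aortic and mitral valves has some basis, since Section 1.5.1 reports that the abnormal-echocardiogram events in Study 1503 were all trace mitral or trace aortic. That may explain strictness on those valves, which is not at fault here. It gives no reason to ignore a Level 2 or 3 finding on the other two.

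A reader might go further and infer that the protocol contains two conflicting rules on ECHO timing. The documents do not support that. Table 8 sets oversight steps, Table 5 and the skipped-visit sentence concern follow-up after treatment, and Section 4.4 governs discontinuation. None of them fixes the on-treatment interval.

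**Conclusion.** The point holds as an omission. In one contingency rule, two of the four graded valves are not tested, and the result does not match the protocol's own ranking of findings. The consequence is at most 48 extra days between ECHOs on the 6-monthly schedule. It requires all of the following: isolated moderate or severe tricuspid or pulmonary regurgitation, no aortic regurgitation, at most trace mitral regurgitation, PASP below 30 mmHg, a decision to continue treatment without more frequent ECHO, and inability to travel because of COVID-19.

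The number of subjects affected cannot be computed, though it is probably very small. A reader might treat the Study 1503 report as zero cases in 330 and put a confidence limit on it. That is not supported: the report describes adverse event terms in Dravet syndrome, gives no tricuspid or pulmonary grades, and does not cover Lennox-Gastaut syndrome.

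Sample size, endpoints and analyses are untouched. Severity is minor. Confidence is high for the gap in the text, not for its practical effect.

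**What to change.** In Appendix 6, item 4, add to the 3-month condition: *and no Level 2 or greater finding on any valve (Table 8)*. Add to the 6-week sentence: *or any Level 2 or greater finding on any valve (Table 8)*. The existing limits for trace aortic and mild mitral regurgitation stay as they are.

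The cost is one clause in each of two sentences. No new data are needed, because the central reader already grades all four valves. The downside is that a few ECHOs would have to be done sooner under travel restrictions. Appendix 6 already provides for that when an ECHO cannot be done in time at the authorized site: "the Sponsor may approve administration of the ECHO at an alternative facility to minimize subject's need for travel".
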